5.8.3.1. Physical Examinations

Physical examination results at each time point will be summarized; shifts between baseline and a subsequent study visit in physical examination findings to will also be presented. All physical examination findings will be presented in a data listing.

5.8.4. Concomitant Medications

Concomitant medications will be coded using the WHO Drug dictionary. Results will be tabulated by Anatomic Therapeutic Class (ATC) and preferred term.

The use of concomitant medications will be included in by-subject data listing.

Previous medications are defined as medications reported with a stop date prior or equal to the date of inclusion. In case of partial/missing stop date the following rules will be applied:

- If only the day is missing: month and year of stop date will be used to determine whether the medication is prior or concomitant
- If day and month are missing: the year of stop date will be used to determine whether the medication is prior or concomitant
- If the stop date is missing the medication will be considered as prior and concomitant

All other medications reported will be considered as concomitant. Previous and concomitant medications will be described in each treatment group according to their therapeutic class (ATC) and preferred term (PT) (WHO Drug Dictionary, version of March 2013).

The previous and concomitant medications will be summarized by treatment group in the ITT population.:

- The number and percentage of patients presenting at least one previous medication will be described in each treatment group.
 - The previous medication will then be presented per ATC and PT in a frequency table in each treatment group.
- The number and percentage of patients presenting at least one concomitant medication will be described in each treatment group.
 - The concomitant medication will then be presented per ATC and PT in a frequency table, in each treatment group.

The medications given for type II diabetes will be presented.

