7.2 Exclusion criteria

- Patients with M3 AML of FAB classification (APL, Acute Promyelocytic Leukemia))
- Patients with AML involving chromosome 16 abnormalities or translocation (8:21) (CBF-AML)
- Patient with Secondary AML subsequent to prior malignant blood disorder such as:
 - Myelodysplastic syndrome diagnosed more than 6 months before study entry
- Myeloproliferative syndrome
- Prior therapy to AML (standard therapy or investigational agents)
- Inadequate organ functions:
 - Uncontrolled or severe cardiovascular disease including myocardial infarction within 6 months of enrollment, New York Heart Association (NYHA) Class III or IV heart failure, uncontrolled angina, clinically significant pericardial disease, or cardiac amyloidosis.
 - Serum creatinine concentration > 2x ULN (Upper Limit of Normal laboratory ranges),
 - $\circ~$ AST or ALT levels > 3.5x ULN or > 5x ULN , if related to AML
 - Total bilirubin levels > 2x ULN
 - \circ INR > 1.5, unless patient under chronic treatment with anticoagulants (in this case, INR should be within expected ranges for the specific condition)
 - Insulin-dependent or uncontrolled diabetes mellitus
- Concurrent malignancies other than AML requiring chemotherapy

- Severe active infection, HIV seropositivity, or known active type B or C viral hepatitis
- Known or suspected hypersensitivity or intolerance to mannitol
- Breastfeeding or lactating women

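### SAP 5.8.4 classifies medications by stop date alone, so a drug started after inclusion and still open at the end of data collection is counted in the prior-medication table

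*SAP*

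**What the plan says.** All the classification rules are in SAP 5.8.4 (Concomitant Medications).

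- Definition of prior: "Previous medications are defined as medications reported with a stop date prior or equal to the date of inclusion".
- Stop day missing: "month and year of stop date will be used to determine whether the medication is prior or concomitant".
- Stop day and month missing: "the year of stop date will be used to determine whether the medication is prior or concomitant".
- Stop date missing altogether: "If the stop date is missing the medication will be considered as prior and concomitant".
- Everything else: "All other medications reported will be considered as concomitant".

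The prior category is reported by arm in the ITT population: "The previous medication will then be presented per ATC and PT in a frequency table in each treatment group". In the output list of SAP 8.1 this is Table 14.1.5.1, with concomitant medications in Table 14.1.5.2. The same section adds: "The medications given for type II diabetes will be presented". It does not say whether that display is split into prior and concomitant.

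Neither the rest of the SAP nor the protocol adds a start-date condition or a rule for drugs still being taken when data collection ends.

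**The concern.** A prior-medication table describes patients at baseline, so its content should be settled by inclusion. Under the rule for a missing stop date it is not. Whether a drug begun on study counts as prior depends on whether someone later recorded that it stopped.

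Such records will exist. Protocol 8.10 has changes in concomitant medication recorded from visit 1 onwards, and Protocol Table 6 continues this at end of treatment and in follow-up. Survival is expected to be short (the SAP Introduction works from a median OS of about 6.4 months), so some drugs will still be open when a patient dies or the data are cut.

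The trial has one setting where the direction could mislead. Protocol 9.5 warns that L-asparaginase may raise blood glucose, SAP 5.8.1 gives diabetogenic events a special focus, and diabetes medications are singled out for presentation. If glucose-lowering treatment is started more often in one arm and left open, Table 14.1.5.1 would show a difference between arms that did not exist at baseline.

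**Working it through.** There is no planned figure to reproduce. The check applies the written rule to each pattern of start and stop dates.

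**Inputs.** The reference date is inclusion (SAP 5.8.4). Prior means stopped on or before inclusion. A missing stop date gives both categories. Everything else is concomitant. The last column applies the change described under the fix.

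| Start | Stop | SAP rule, read literally | With the change |
|---|---|---|---|
| Before inclusion | On or before inclusion | Prior | Prior |
| Before inclusion | Known, after inclusion | Concomitant only | Concomitant only |
| Before inclusion | Missing, not recorded as ongoing | Both | Both |
| Before inclusion | Recorded as ongoing | Both, if ongoing is read as missing | Concomitant only (not stopped) |
| After inclusion | Known | Concomitant only | Concomitant only |
| After inclusion | Missing or ongoing | **Both** | Concomitant only |
| Unknown or too partial | Missing | Both | Both |

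**Reasoning.** Compare the two rows that start after inclusion. They differ only in whether a stop date was entered, yet only the open record is counted as prior. A drug that started after inclusion cannot have stopped on or before it, so the rule for missing dates contradicts the SAP's own definition. Dual status is a reasonable default when timing is unknown. Here the start date has already settled it.

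**Illustration of size, on assumptions only.** Let start times be uniform over a follow-up of T days and durations exponential with mean m days. The share of on-study starts still open at T is then

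(1/T) ∫₀ᵀ e^(−u/m) du = (m/T)(1 − e^(−T/m)).

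Take T = 6.4 × 30.4 = 194.6 days:

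- m = 14: 0.072
- m = 30: 0.154
- m = 90: 0.409
- m = 180: 0.611

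The values of m, the uniform starts and the common follow-up are assumptions; 6.4 months is a median OS and not a medication-collection period. The result is the share of on-study records left open. It is not the error in a table that counts patients by ATC class and preferred term.

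**The case against.** The strongest reply is that the bullet is a missing-data rule, and an ongoing drug is not missing a stop date. The sponsor's SAE form (Protocol Appendix 7) has separate start, stop and ongoing fields for concomitant drugs. If the eCRF does the same, programmers could send flagged drugs to the residual category, which is concomitant only. This stands as a limit on how often the error would occur in practice. It does not rescue the text: the eCRF is not among the documents, and the SAP never draws the distinction.

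Several stronger readings are tempting, and the documents do not support them.

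- *New glucose-lowering treatment would be hidden as pre-existing.* The drug also stays in the concomitant table, so no on-study use is lost. Hyperglycaemia is assessed through adverse events (SAP 5.8.1) and glycaemia over time (SAP 5.8.2.1), and neither uses this split.
- *New insulin would look like a breach of the exclusion* "Insulin-dependent or uncontrolled diabetes mellitus". Under SAP 4.2, violations come from a separate list finalised at data review before lock. Nothing derives them from Table 14.1.5.1, and no document names insulin as the treatment for GRASPA-related hyperglycaemia.
- *An antineoplastic given after progression would be counted as prior therapy.* Subsequent AML therapy is its own scheduled item (Protocol 8.10 and Table 6). Nothing shows that it passes through this rule.
- *A long-standing drug stopped on study is wrongly left out of the prior table.* Under the SAP's definition it is correctly concomitant only. Calling it wrong would substitute a different definition of prior.

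It is also fair to say that the tables are descriptive and that SAP 5.5 plans no formal baseline comparisons.

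**Conclusion.** The point holds as an error in a stated rule. Followed as written, SAP 5.8.4 puts drugs known to have started after inclusion into a baseline table by arm whenever no stop date is recorded, against its own definition of prior.

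The consequence is minor: the content of Table 14.1.5.1, and possibly the diabetes display if that is split. OS, PFS, response, adverse-event summaries and the concomitant table do not change.

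The size is not determinable from the documents. The illustrative shares of 7% to 61% rest wholly on assumed durations, and an ongoing flag in the eCRF could reduce the error further. A difference between arms is possible but has not been shown. The conclusion does not depend on those percentages; it follows from the wording of the rule.

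**What to change.** Keep inclusion as the reference date. Moving to first study dose would leave randomised but untreated patients undefined; the SAP expects such patients (Listing 14.1.2.3), and these tables are on the ITT population. Amend SAP 5.8.4 to state that:

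1. A medication with a start date after inclusion is concomitant only, whatever its stop date.
2. A medication recorded as ongoing is treated as not stopped.
3. A missing stop date gives dual status only when the start date is on or before inclusion, or is missing or too partial to decide.

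Use the same rule for the type II diabetes medications if that display is split into prior and concomitant.

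The cost is a few sentences and one changed derivation, with no new data. The SAP is to be signed before database lock, so the change belongs there. Records whose start cannot be placed remain in both tables, which is the cautious choice.

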6. CHANGES TO PLANNED ANALYSES

Initially, this study was designed with Progression Free Survival as its primary endpoint. However, the protocol definition of PFS only considered death due to progression. It was recognised that this was not in line with regulatory guidance where death from any cause is included in the endpoint and the definition of PFS was therefore modified. Based on recommendations from the AML Advisory Board (meeting conducted on 24th January 2017) the primary endpoint was changed from PFS to overall survival.

A planned interim analysis for futility was not conducted.

7. REFERENCES

8. CLINICAL STUDY REPORT APPENDICES

8.1. Statistical Tables, Figures, and Listings to be Generated

Table/Figure Number	Output Title	Analysis Set
	Patient Information	
14.1.1.1	Overall Patients Disposition	All Patients
14.1.1.2	Patients Disposition by Investigator Centre	All Patients
	Protocol Deviations	
14.1.2.1	Summary of Deviations Related to Inclusion/Exclusion Criteria	ITT
14.1.2.2	Summary of Major Protocol Deviations – Reasons for Exclusion From Per Protocol Population	ITT
14.1.2.3	Listing of Patients Randomized but not Treated	ITT
	Demographic Data and Baseline Characteristics	
14.1.3.1	Patient Demographics and Baseline Characteristics	ITT
14.1.3.2	Disease Characteristics and AML Cancer History	ITT
	Prior Related Therapies	
	Medical History Related to Other Diseases	

Table/Figure Number	Output Title	Analysis Set
14.1.4.1	Summary of Medical History – Previous Condition	ITT
14.1.4.2	Summary of Medical History – Ongoing Condition	ITT
	Prior and Concomitant Medications	
14.1.5.1	Summary of Prior Medications	ITT
14.1.5.2	Summary of Concomitant Medications	ITT
	Treatment Compliance and Exposure	
14.1.6.1	Summary of Study Duration	Safety
	Treatment Exposure	
14.1.6.2.1	Summary of Exposure to GRASPA and Low Dose Cytarabine and Dose Intensity	Safety
14.1.6.2.2	Compliance, Dose Reductions and Interruptions of GRASPA and Low Dose Cytarabine	Safety
14.1.6.2.3	Listing of Patients with at Least One Dose Reduction or Interruption of GRASPA and Low Dose Cytarabine	Safety
	Efficacy Data	
14.2.1.1.1.1	Summary of Overall Survival by Treatment Group	ITT

Table/Figure Number	Output Title	Analysis Set
14.2.1.1.1.2	Summary of Overall Survival by Treatment Group	PP
14.2.1.1.2.1	Overall Survival by Treatment Group – Kaplan Meier Curves	ITT
14.2.1.1.2.2	Overall Survival by Treatment Group – Kaplan Meier Curves	PP
14.2.1.1.3.1	Summary of Overall Survival by Treatment Group – Cox PH Model with Prognostic Factors	ITT
14.2.1.1.3.2	Summary of Overall Survival by Treatment Group – Cox PH Model with Prognostic Factors	PP
14.2.1.1.4.1	Forest Plot of OS Hazard Ratios – Subgroup Analyses	ITT
14.2.1.1.4.2	Forest Plot of OS Hazard Ratios – Subgroup Analyses	PP
14.2.1.2.1.1	Summary of Disease Response and Duration of Response by Treatment Group	ITT
14.2.1.2.1.2	Summary of Disease Response and Duration of Response by Treatment Group – Subgroup Analyses	ITT
14.2.1.3.1.1	Summary of Progression Free Survival by Treatment Group	ITT
14.2.1.3.1.2	Summary of Progression Free Survival by Treatment Group	PP
14.2.1.3.2.1	Progression Free Survival by Treatment Group – Kaplan Meier Curves	ITT

Table/Figure Number	Output Title	Analysis Set
14.2.1.3.2.2	Progression Free Survival by Treatment Group – Kaplan Meier Curves	PP
14.2.1.3.3.1	Summary of Progression Free Survival by Treatment Group – Cox PH Model with Prognostic Factors	ITT
14.2.1.3.3.2	Summary of Progression Free Survival by Treatment Group – Cox PH Model with Prognostic Factors	PP
14.2.1.3.4.1	Forest Plot of Progression Free Survival Odds Ratios – Subgroup Analyses	ITT
14.2.1.3.4.2	Forest Plot of Progression Free Survival Odds Ratios – Subgroup Analyses	PP
14.2.1.4.1	Summary of Relapse Free Survival by Treatment Group	ITT
14.2.1.4.2	Relapse Free Survival by Treatment Group – Kaplan Meier Curves	ITT
14.2.1.5	Summary of Transfusion Needs by Treatment Group	ITT
14.2.1.6.1	Summary of Biomarkers	ITT
Figure 14.2.1.6.2	Biomarkers Over Time – Spaghetti Plots	ITT
	PK and PD Parameters	
14.2.9.1	PK and PD Parameters – Plasma and Blood – Summary Statistics Over Time	Safety

Table/Figure Number	Output Title	Analysis Set
14.2.9.2	PK and PD Parameters – Plasma and Blood – Patients with Asparagine Depletion	Safety
14.2.9.3	PK and PD Parameters – Immunogenicity	Safety
14.2.9.4	Summary of Biomarker Cytogenetic Testing	Safety
14.2.9.5	Summary of Bone Marrow Tumor Cell Parameters	Safety
	Quality of Life Questionnaires	
14.2.10	QLQ-C30 Absolute and Changes From Baseline	ITT
	Number of Hospitalizations	
14.2.11	Summary of Hospitalizations by Treatment Group	ITT
	Safety Data	
	Adverse Events	
14.3.1.1.1	Summary Analysis of Incidence of Treatment Emergent Adverse Events	Safety
14.3.1.1.2	Summary Analysis of Incidence of Treatment-Related Treatment Emergent Adverse Events	Safety
14.3.1.1.3	Summary Safety Analysis of GRASPA in combination with low-dose cytarabine	ITT

Table/Figure Number	Output Title	Analysis Set
14.3.1.2.1	Incidence of Treatment Emergent Adverse Events by Preferred Term	Safety
14.3.1.2.2	Incidence of Treatment Related Treatment Emergent Adverse Events by Preferred Term	Safety
14.3.1.2.3	Incidence of Treatment Emergent Adverse Events with Toxicity Grade of 3 or 4 by Preferred Term	Safety
14.3.1.2.4	Incidence of Treatment Related Treatment Emergent Adverse Events with Toxicity Grade of 3 or 4 by Preferred Term	Safety
14.3.1.2.5	Incidence of Treatment Emergent Serious Adverse Events by Preferred Term	Safety
14.3.1.2.6	Incidence of Treatment Related Treatment Emergent Serious Adverse Events by Preferred Term	Safety
14.3.1.2.7	Incidence of Treatment Emergent Adverse Events of Special Interest by Preferred Term	Safety
14.3.1.2.8	Incidence of Treatment Emergent Adverse Events of Special Interest with Toxicity Grade of 3 or 4 by Preferred Term	Safety
14.3.1.2.9	Incidence of Treatment Emergent Adverse Events Occurring in at least 5% of Patients in either Treatment Group by MedDRA Preferred Term	Safety
14.3.1.3	Listing of Treatment Emergent Adverse Events Leading to Either GRASPA or Chemotherapy Withdrawal	Safety

Table/Figure Number	Output Title	Analysis Set
	Deaths	
14.3.2.1	Deaths and Deaths within 28 Days After Last IMP Administration	Safety
14.3.2.2	Listing of All Deaths	Safety
	Clinical Laboratory Data	
	Biochemistry	
14.3.3.1.1	Biochemistry – Summary of Shift From Baseline to Worst Post-Baseline Results	
14.3.3.1.2	Biochemistry – Summary Statistics for Clinically Significant Parameters by Treatment Group and Time	
	Hematology	
14.3.3.2.1	Hematology – Summary of Shift From Baseline to Worst Post-Baseline Results	Safety
14.3.3.2.2	Hematology – Summary Statistics for Clinically Significant Parameters by Treatment Group and Time	Safety
	Coagulation	
14.3.3.3.1	Coagulation – Summary of Shift From Baseline to Worst Post-Baseline Results	Safety

Table/Figure Number	Output Title	Analysis Set
14.3.3.3.2	Coagulation – Summary Statistics for Clinically Significant Parameters by Treatment Group and Time	Safety
	Other Safety Parameters	
	Vital Signs Data	
14.3.4.1.1	Vital Signs – Descriptive Statistics for Change From Baseline	Safety
14.3.4.1.2	Vital Signs – Listing of Clinically Significant Values	Safety
14.3.4.2	ECOG Performance Status – Shift From Baseline to Worst Post-Baseline Value	Safety

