3.2. Randomization Methodology

The patients will be randomly and sequentially allocated to either one of the two treatments A or B, and the treatment allocation will be stratified by Eastern Cooperative Oncology Group (ECOG) performance status (PS=0 or 1 versus PS=2). This will ensure balance between the performance groups, which was been identified as a risk factor for early death.

Randomization 1:2 will be performed using Interactive Web Response Services (IWRS).

Randomization group will be confirmed to investigator by e-mail, specifying the treatment arm assigned, namely A or B, as follows:

- A: Low-dose cytarabine
- B: Low-dose cytarabine + GRASPA

Randomization will continue until 123 patients are recruited and receive study treatment.

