3.5.3. Safety Variables

All subjects who received at least one dose of investigational products will be included in the safety analyses. Safety data will be summarized using actual treatment received, regardless of randomized treatment.

Safety and tolerability will be assessed in terms of AEs, SAEs, laboratory data and vital signs which will be collected for all subjects. AEs will be coded according to the Medical dictionary for regulatory activities (MedDRA) version 15.1 or higher. The intensity of AEs will be graded according to the NCI-CTCAE (version 4.0).

AEs, AE leading to study treatment discontinuation, AE related to study treatment, and SAEs will be listed individually by subject, and summarized by System Organ Class (SOC) and Preferred Term (PT) by treatment group. Summary of AEs with NCI-CTCAE grade 3 or 4 and most frequent PT will also be provided.

Specific attention will be given to NCI-CTCAE Grade 3 or 4 of pancreatic toxicity, Grade 3 or 4 of hepatotoxicity, allergic reactions or coagulation disorders, known to be potentially related to L-asparaginase as well as to hypoproteinemia and hyperglycemia/diabetes events.

Specific safety endpoints will include the following:

- 1) Safety of GRASPA in combination with low-dose cytarabine, with specific attention to :
 - a. Grade 3 or 4 of pancreatic toxicity
 - b. Grade 3 or 4 of hepatic toxicity, allergic reaction or coagulation event
 - c. Grade 3 or 4 of hypoproteinemia or hyperglycemia/diabetes
 - d. All other non-hematologic Grade 4 toxicities

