4. SUBJECT POPULATIONS

4.1. Population Definitions

The **intent-to-treat (ITT) population** will comprise all randomized patients in the groups to which they were randomly assigned, regardless of their adherence with the entry criteria, regardless of the treatment they actually received, and regardless of subsequent withdrawal from treatment or deviation from protocol.

The **per-protocol (PP) population** will comprise all patients from the ITT population without any major protocol deviation that have received trial product and have completed at least one course of treatment.

All data analysed on the ITT or PP populations will be summarized using randomized treatment.

The **safety population** will comprise all patients that have received at least one administration of trial products.

All data analysed on the safety population will be summarized using actual treatment received.

The responsibility for defining the study populations and excluding patients from the analysis will be a joint decision by the sponsor, trial statistician, investigator and trial monitor. The patients to be excluded and the reasons for their exclusion must be documented and signed by those responsible prior to database release. The documentation must be stored together with the remaining trial documentation.

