5.8. Safety Analyses

Safety analyses will be conducted using the Safety Population.

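### SAP 8.1 puts one summary safety table (14.3.1.1.3) on the ITT set, contradicting the SAP's own rule that safety is analysed in treated patients by actual treatment

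*SAP*

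**What the plan says.** SAP 8.1 lists output 14.3.1.1.3, "Summary Safety Analysis of GRASPA in combination with low-dose cytarabine", under Safety Data with ITT as its analysis set. It is the only output under that heading labelled ITT. The other adverse event, death, haematology, coagulation, vital-sign and performance-status outputs are labelled Safety, and the two biochemistry rows have no entry.

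The rules in the body of the SAP point elsewhere:

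- SAP 5.8: "Safety analyses will be conducted using the Safety Population".
- SAP 3.5.3, on who is included: "All subjects who received at least one dose of investigational products will be included in the safety analyses".
- SAP 3.5.3, on columns: "Safety data will be summarized using actual treatment received, regardless of randomized treatment".
- SAP 4.1 says that the ITT population "will comprise all randomized patients in the groups to which they were randomly assigned", whatever they received. ITT data are summarised by randomised treatment and Safety data by actual treatment.

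Protocol 15.3.3 repeats both rules of SAP 3.5.3. Protocol 6.2 draws the same line: efficacy by randomised treatment, safety by treatment received. SAP 6, which records changes to planned analyses, does not mention an ITT safety table.

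**The concern.** The two instructions cannot both be followed. A programmer who works from the output list breaks SAP 5.8, and one who works from SAP 5.8 breaks the output list.

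The ITT label changes two things. It adds to the denominators any patient who was randomised but took no study drug. It also moves the columns from actual to randomised treatment. The second change matters here because GRASPA is first given on Day 11, after ten days of cytarabine, so an arm-B patient can be treated and yet have no GRASPA exposure.

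The table's title closely follows the opening of the specific safety endpoint in SAP 3.5.3, "Safety of GRASPA in combination with low-dose cytarabine, with specific attention to", which goes on to name the grade 3 or 4 toxicities of interest. If this is the table that brings that endpoint together, its percentages would disagree with the adverse event tables beside it, and a reader of the study report would not be told why.

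**Working it through.** The plan states no figure that could be reproduced on this point. The check is a comparison of text, followed by arithmetic on assumed counts.

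**1. The label against the rules**

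| Feature | As listed for 14.3.1.1.3 (ITT, SAP 4.1) | As required by SAP 3.5.3, 4.1 and 5.8 and protocol 15.3.3 |
|---|---|---|
| Who is counted | All randomised patients | Patients with at least one dose |
| Columns | Randomised arm | Actual treatment |

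**2. Can the two sets differ?** The documents allow for it but give no number.

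- SAP 8.1 plans output 14.1.2.3, "Listing of Patients Randomized but not Treated".
- SAP 3.2: "Randomization will continue until 123 patients are recruited and receive study treatment". The number randomised can therefore exceed the number treated.
- Protocol 8.4 foresees an arm-B patient who is switched to another treatment before the first GRASPA infusion.

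**3. Dilution from never-treated patients**

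Inputs: 41 control and 82 GRASPA patients, the planned arm sizes in SAP 5.1, taken here as the treated numbers. The number never treated, m, is assumed. Untreated patients are assumed to contribute no events.

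Factor applied to the rate = treated / (treated + m). For arm B:

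| m | Factor | Relative fall | Example with 16 events (assumed) |
|---|---|---|---|
| 0 | 82/82 | 0% | 19.5% |
| 1 | 82/83 | 1.2% | 19.3% |
| 2 | 82/84 | 2.4% | 19.0% |
| 4 | 82/86 | 4.7% | 18.6% |
| 8 | 82/90 | 8.9% | 17.8% |

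**4. Effect on the GRASPA:control rate ratio**

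Multiplier = [82/(82 + m_B)] / [41/(41 + m_A)].

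- None untreated: 1, no change.
- One in each arm: (82/83)/(41/42) = 0.988/0.976 = 1.012, up 1.2%.
- Two control, six GRASPA: (82/88)/(41/43) = 0.932/0.953 = 0.977, down 2.3%.
- Six control, two GRASPA: (82/84)/(41/47) = 0.976/0.872 = 1.119, up 12%.

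The direction depends entirely on which arm has the untreated patients.

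**5. Effect of grouping by randomised arm**

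Suppose all 82 arm-B patients start cytarabine, c of them never receive GRASPA, and all 16 assumed events occur in GRASPA recipients. The GRASPA column as randomised shows 16/82 = 19.5%. As treated it shows 16/(82 - c):

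- c = 2: 16/80 = 20.0%
- c = 4: 16/78 = 20.5%
- c = 8: 16/74 = 21.6%

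This effect needs no untreated patient at all. With c = 0 it vanishes.

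**The case against.** The strongest reply is that this is a clerical slip in an appendix. The body of the SAP is consistent about treated patients. The output list has other slips, such as PFS forest plots headed as odds ratios and tumour-lesion listings in a leukaemia trial. SAP 1 puts the table shells in a separate document, which may already have the right set. That may be so. But SAP 8.1 is where the analysis set of each output is stated, and nothing in the SAP says that SAP 5.8 overrides it.

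Four further points stand, and they limit the finding:

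- **Identity of the table.** A reader might take 14.3.1.1.3 to be the special-attention endpoint table. That is an inference from the title. The title names no grade and no toxicity, and it fits the general safety objective in SAP 2.1.2 almost as well.
- **Reach.** A reader might infer that the trial's key toxicity rates would be reported too low. The documents do not support that. Tables 14.3.1.2.3 and .4 (grade 3 or 4 events) and 14.3.1.2.7 and .8 (events of special interest) use the Safety set. So does the diabetogenic and pancreatic summary in SAP 5.8.1, through SAP 5.8. At most one summary table is affected.
- **Number untreated.** A listing and a recruitment target allow for untreated patients without showing that there are any. SAP 5.2.7 says withdrawn subjects were not replaced, which sits awkwardly with continued randomisation. Both arms start cytarabine on Day 1, so if cytarabine counts as a trial product, only patients who never start it leave the Safety set.
- **Distortion between arms.** A reader might quote the 12% shift in the rate ratio. It is one chosen imbalance; others give 1.2% upwards, 2.3% downwards or nothing. Even there the absolute change is slight: 4/41 = 9.8% becomes 4/47 = 8.5%, against an exact 95% interval of 2.7% to 23.1% for 4/41.

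No efficacy decision turns on this table. SAP 5.1 bases the judgement of promise on the OS hazard ratio.

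**Conclusion.** The contradiction is explicit and should be corrected: SAP 8.1 assigns 14.3.1.1.3 to ITT, while SAP 3.5.3 and 5.8 and protocol 15.3.3 require treated patients by actual treatment, and no reason for the exception is given. It affects one summary table, in both its denominators and its columns.

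The consequence cannot be sized from the documents and is probably small. With 1 to 8 never-treated arm-B patients, arm-B rates fall by 1.2% to 8.9% in relative terms. With 2 to 8 arm-B patients who received only cytarabine, a GRASPA rate of 20.0% to 21.6% would be shown as 19.5%. These figures rest on assumed counts, on treated numbers equal to the planned 41 and 82, and on the added patients contributing no events. Protocol 11.1.2.2 collects events from consent, so the last assumption may not hold exactly. If every patient was treated as randomised, the two versions coincide.

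**What to change.** In SAP 8.1, change the analysis set of 14.3.1.1.3 from ITT to Safety, grouped by actual treatment received, with the same columns and denominators as 14.3.1.2.1 to 14.3.1.2.9. If an ITT version is wanted as a supplement, say so, label it as such and give the reason. Check that the separate table shells agree. Randomised-but-untreated patients remain visible in 14.1.2.3. The blank analysis set for 14.3.3.1.1 and 14.3.3.1.2 can be filled in at the same time.

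The cost is one cell in the output list, changed before the database is locked. It needs no new data and no new analysis. If any patients were untreated or missed GRASPA, some percentages in this table will be slightly higher than under the ITT label.
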